3.2 Exclusion criteria

Subjects should not enter the study if any of the following exclusion criteria are fulfilled:

1. Involvement in the planning and/or conduct of the study (applies to both AstraZeneca staff and/or staff at the study site).
2. Treatment with any of the following:
 - Treatment with an EGFR-TKI (eg, erlotinib, gefitinib, icotinib or afatinib) within 8 days or approximately 5x half-life, whichever is the longer, of the first dose of study treatment. (If sufficient washout time has not occurred due to schedule, an alternative appropriate washout time based on known duration and time to reversibility of drug related adverse events could be agreed upon by AstraZeneca and the Investigator).
 - Any cytotoxic chemotherapy, investigational agents or other anticancer drugs from a previous treatment regimen or clinical study within 14 days of the first dose of study treatment
 - Previous treatment with AZD9291, or a 3rd generation EGFR TKIs (eg, CO-1686)
 - Major surgery (excluding placement of vascular access) within 4 weeks of the first dose of study treatment
 - Radiotherapy treatment to more than 30% of the bone marrow or with a wide field of radiation within 4 weeks of the first dose of study treatment
 - Patients currently receiving (or unable to stop use at least 1 week prior to receiving the first dose of study treatment) medications or herbal supplements known to be potent inhibitors or inducers of CYP3A4 ([Appendix E](#))
 - Treatment with an investigational drug within five half-lives of the compound
3. Any unresolved toxicities from prior therapy greater than Common Terminology Criteria for Adverse Events (CTCAE) grade 1 at the time of starting study treatment with the exception of alopecia and grade 2, prior platinum-therapy related neuropathy.
4. Spinal cord compression or brain metastases unless asymptomatic, stable and not requiring steroids for at least 4 weeks prior to start of study treatment.
5. Any evidence of severe or uncontrolled systemic diseases, including uncontrolled hypertension and active bleeding diatheses, which in the investigator's opinion

makes it undesirable for the patient to participate in the trial or which would jeopardise compliance with the protocol, or active infection including hepatitis B, hepatitis C and human immunodeficiency virus (HIV). Screening for chronic conditions is not required. However, for patients participating biomarker/genetic research and from outside of China, HBV, HCV and HIV tests are needed for sample shipment purpose, and results should be negative.

6. Refractory nausea and vomiting, chronic gastrointestinal diseases, inability to swallow the formulated product or previous significant bowel resection that would preclude adequate absorption of AZD9291.
7. Any of the following cardiac criteria:
 - Mean resting corrected QT interval (QTc) >470 msec, obtained from 3 electrocardiograms (ECGs).
 - Any clinically important abnormalities in rhythm, conduction or morphology of resting ECG eg, complete left bundle branch block, third degree heart block, second degree heart block, PR interval >250 msec.
 - Any factors that increase the risk of QTc prolongation or risk of arrhythmic events such as heart failure, hypokalaemia, congenital long QT syndrome, family history of long QT syndrome or unexplained sudden death under 40 years of age in first degree relatives or any concomitant medication known to prolong the QT interval.
8. Past medical history of interstitial lung disease, drug-induced interstitial lung disease, radiation pneumonitis which required steroid treatment, or any evidence of clinically active interstitial lung disease.
9. Inadequate bone marrow reserve or organ function as demonstrated by any of the following laboratory values:
 - Absolute neutrophil count <1.5x10⁹/L
 - Platelet count <100x10⁹/L
 - Haemoglobin <90 g/L
 - Alanine aminotransferase >2.5 times the upper limit of normal (ULN) if no demonstrable liver metastases or >5 times ULN in the presence of liver metastases
 - Aspartate aminotransferase >2.5 times ULN if no demonstrable liver metastases or >5 times ULN in the presence of liver metastases
 - Total bilirubin >1.5 times ULN if no liver metastases or >3 times ULN in the presence of documented Gilbert's Syndrome (unconjugated hyperbilirubinaemia) or liver metastases
 - Creatinine >1.5 times ULN concurrent with creatinine clearance <50 ml/min (measured or calculated by Cockcroft and Gault equation); confirmation of creatinine clearance is only required when creatinine is >1.5 times ULN.

10. History of hypersensitivity to active or inactive excipients of AZD9291 or drugs with a similar chemical structure or class to AZD9291.
11. Males and females of reproductive potential who are not using an effective method of birth control and females who are pregnant or breastfeeding or have a positive (urine or serum) pregnancy test prior to study entry.
12. Judgment by the investigator that the patient should not participate in the study if the patient is unlikely to comply with study procedures, restrictions and requirements.

In addition, the following is considered a criterion for exclusion from the exploratory genetic research:

13. Prior allogeneic bone marrow transplant.
14. Non-leukocyte depleted whole blood transfusion within 120 days of genetic sample collection.
15. Other co-existing malignancies or malignancies diagnosed within the last 5 years, with the exception of basal cell carcinoma or cervical cancer in situ.

Procedures for withdrawal of incorrectly enrolled subjects see Section 3.4.

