3.5 Restrictions

The following restrictions apply while the patient is receiving study treatment and for the specified times before and after:

1. Females of child-bearing potential should use reliable methods of contraception from the time of screening until 6 weeks after discontinuing study treatment. Acceptable methods of contraception include total sexual abstinence, tubal ligation, hormonal contraceptives that are not prone to drug-drug interactions [IUS Levonorgestrel Intra Uterine System (Mirena), Medroxyprogesterone injections (Depo-Provera)], copper-banded intra-uterine devices and vasectomised partner. All hormonal methods of contraception should be used in combination with the use of a condom by their male sexual partner for intercourse.
2. Male patients should be asked to use barrier contraceptives (ie, by use of condoms) during sex with all partners during the trial and for a washout period of 4 months. Male patients should avoid procreation for 4 months after completion of trial treatment. Patients should refrain from donating sperm from the start of dosing until 4 months after discontinuing study treatment. If male patients wish to father children they should be advised to arrange for freezing of sperm samples prior to the start of study treatment.
3. Once enrolled all patients must try to avoid concomitant use of medications, herbal supplements and/or ingestion of foods with known potent inducers of CYP3A4 whenever feasible, but patients may receive any medication that is clinically indicated for treatment of adverse events. Such drugs must have been discontinued for an appropriate period before they enter screening and for a period of 3 months after the last dose of AZD9291. All concomitant medications should be captured on

the eCRF. Guidance on medicines to avoid, medications that require close monitoring and on washout periods is provided (see [Appendix E](#)).

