5.1 Efficacy assessments

5.1.1 RECIST 1.1

All imaging assessments including unscheduled visit scans should be collected on an ongoing basis and sent to an AstraZeneca (AZ) appointed Clinical Research Organisation (CRO) to enable independent central analyses prior to RECIST modules freeze time (24 months post LSFD).

For both Independent Central Review (ICR) and investigator review RECIST 1.1 criteria will be used to assess each patient's tumour response to treatment and allow calculation of ORR, PFS, DCR, DoR, and assess tumour shrinkage. The RECIST 1.1 guidelines for measurable, non-measurable, target and non-target lesions and the objective tumour response criteria [CR (complete response), PR (partial response), SD (stable disease) or PD (progression of disease)] are presented in [Appendix C](#). For ORR, a visit response of CR or PR must be confirmed by a later scan conducted at least 4 weeks after the initial response is observed. See [Section 4](#) for considerations related to RECIST 1.1 assessments.

The methods used at baseline for assessment of tumour burden [CT or MRI scans of chest and abdomen (including liver and adrenal glands)] must be used at each subsequent follow-up assessment. Any other areas of disease involvement should be additionally investigated based on the signs and symptoms of individual patients. CT/MRI scan of the brain should be performed in patients with known or suspected brain metastases. The baseline assessment should be performed within 28 days prior to treatment start. Assessments to be performed every 6 weeks relative to first dose until objective disease progression. It is important to follow the assessment schedule as closely as possible. If scans are performed outside of the scheduled visit ± 1 week window interval and the patient has not progressed, every attempt should be made to perform the subsequent scans at their scheduled time points. Any other sites at which new disease is suspected should also be appropriately imaged.

If the investigator is in doubt as to whether progression has occurred, particularly with response to non-target lesions (NTLs) or the appearance of a new lesion, it is advisable to continue treatment until the next scheduled assessment or sooner if clinically indicated and reassess the patient's status. If repeat scans confirm progression, then the date of the initial scan should be declared as the date of progression.

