APPENDIX E GUIDANCE REGARDING POTENTIAL INTERACTIONS WITH CONCOMITANT MEDICATIONS

Guidance regarding potential interactions with concomitant medications

The use of any natural/herbal products or other “folk remedies” should be discouraged, but use of these products, as well as use of all vitamins, nutritional supplements, and all other concomitant medications must be recorded in the eCRF.

1. DRUGS INDUCING CYP3A4 METABOLISM THAT ASTRAZENECA STRONGLY RECOMMEND ARE NOT COMBINED WITH AZD9291

AZD9291 is metabolised by CYP3A4 and CYP3A5 enzymes.

A drug-drug interaction study of AZD9291 evaluated in patients showed that there is potential for AZD9291 being a victim when co-administered with strong inducers of CYP3A4 (AZD9291 concentrations are decreased when co-dosed with rifampicin).

The following potent inducers of CYP3A4 must not be used during this study for any patient receiving AZD9291.

Table 14 Drugs inducing CYP3A4

Contraindicated drugs	Withdrawal period prior to AZD9291 start
Carbamazepine, phenobarbital, phenytoin Rifampicin, rifabutin, rifapentin St John’s Wort	3 weeks
Phenobarbitone	5 weeks

This list is not intended to be exhaustive, and a similar restriction will apply to other agents that are known to strongly modulate CYP3A4 activity. Appropriate medical judgment is required. Please contact AstraZeneca with any queries you have on this issue.

2. MEDICINES WHOSE EXPOSURES MAY BE AFFECTED BY AZD9291 THAT ASTRAZENECA CONSIDERS MAY BE ALLOWED WITH CAUTION

AZD9291 may increase the concentrations of sensitive BCRP substrate (concentrations of sensitive BCRP substrate, rosuvastatin is increased).

Table 15 Exposure, pharmacological action and toxicity may be increased by AZD9291

Warning of possible interaction	Advice
Rosuvastatin	Drugs are permitted but caution should be exercised and patients monitored closely for possible drug interactions. Please refer to full prescribing information for all drugs prior to co-administration with AZD9291.
Sulfasalazine doxorubicin, daunorubicin, topotecan	

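### The 1-week inducer stop in exclusion 2 is shorter than every withdrawal period in the Appendix E table it cites, and section 3.5 adds a third, unaligned washout statement

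*Protocol*

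**What the plan says.** Three places in the Protocol deal with washout of potent CYP3A4 inducers before treatment.

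- **Section 3.2, criterion 2.** One bullet covers potent CYP3A4 inhibitors and inducers together, including herbal products. It excludes patients who take them or are "unable to stop use at least 1 week prior to receiving the first dose of study treatment", and refers to Appendix E.
- **Appendix E, section 1, Table 14.** The period column is headed "Withdrawal period prior to AZD9291 start". The entries "Carbamazepine, phenobarbital, phenytoin Rifampicin, rifabutin, rifapentin" and St John's Wort have 3 weeks. "Phenobarbitone" has its own row with 5 weeks. The section explains that "AZD9291 concentrations are decreased when co-dosed with rifampicin".
- **Section 3.5, item 3.** Potent inducers have to be stopped for a suitable but unquantified time before the patient enters screening. The item closes with: "Guidance on medicines to avoid, medications that require close monitoring and on washout periods is provided", citing Appendix E.

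Two other parts of the text bear on how these are read. The EGFR-TKI bullet of criterion 2 has two candidate periods and says which applies: "within 8 days or approximately 5x half-life, whichever is the longer, of the first dose of study treatment". Sections 3 and 3.4 allow no exceptions to the eligibility criteria.

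**The concern.** The only number in the eligibility criterion fits none of the inducers in the table that the criterion cites. Eligibility is strict, so the criterion's number decides who may be dosed. Table 14 is not itself a criterion.

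A site that applies criterion 2 as worded can accept a patient whom Table 14 says should not yet start. A second site that works from Table 14 would delay the same patient. The table's periods are there because strong inducers lower AZD9291 exposure, so what is at stake is consistent eligibility and protection of exposure early in treatment.

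Table 14 also appears to list one drug twice with different periods. By common nomenclature phenobarbital (3 weeks) and phenobarbitone (5 weeks) are the same substance. The Protocol does not say so.

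**Working it through.** No sample-size, power or error-rate figure is involved. The check compares the stated periods.

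**Inputs**

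| Source | Period | Counted back from |
|---|---|---|
| Section 3.2, criterion 2 | at least 1 week = 7 days | first dose |
| Appendix E Table 14, seven entries | 3 weeks = 21 days | AZD9291 start |
| Appendix E Table 14, phenobarbitone | 5 weeks = 35 days | AZD9291 start |
| Section 3.5, item 3 | no number | entry to screening |

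Let s be the whole number of days from the last inducer dose to the first AZD9291 dose.

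**Step 1. How many entries exceed the criterion.** The 3-week entries are carbamazepine, phenobarbital, phenytoin, rifampicin, rifabutin, rifapentin and St John's Wort (7). With phenobarbitone there are 8. Since 21 > 7 and 35 > 7, 8 of 8 entries exceed 1 week. If phenobarbital and phenobarbitone are one drug, that is 7 of 7 drugs.

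**Step 2. Where the two rules disagree.** Criterion 2 is passed if s ≥ 7. Table 14 is met if s ≥ 21, or s ≥ 35 for phenobarbitone.

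- 3-week inducers: 7 ≤ s ≤ 20, which is 20 − 7 + 1 = 14 stop dates. The largest shortfall is 21 − 7 = 14 days.
- Phenobarbitone: 7 ≤ s ≤ 34, which is 34 − 7 + 1 = 28 stop dates. The largest shortfall is 35 − 7 = 28 days.
- Example: a patient who stopped rifampicin 10 days before first dose passes criterion 2 and is 21 − 10 = 11 days short of Table 14.

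**Step 3. The duplicate entry.** Taking the two names as one drug, the rows give opposite answers for 21 ≤ s ≤ 34, which is 34 − 21 + 1 = 14 stop dates.

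**Step 4. Whether another passage settles it.** Section 3.5 item 3 is mandatory about stopping inducers and names Appendix E, so it goes part of the way. But it states no number, describes Appendix E as guidance, and counts from screening, whereas criterion 2 and Table 14 count from the start of treatment. It does not say which period prevails. The inducer bullet lacks the longer-of-two wording that the EGFR-TKI bullet has.

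These date counts show where the rules part. They do not measure a clinical or statistical consequence.

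**The case against.** The strongest reply is that there is no contradiction. One week is a minimum for a broad class, and Table 14 adds longer periods for named drugs. The table says it is not exhaustive, asks for medical judgment and invites queries to the sponsor, so a general minimum is still needed for unlisted agents. Section 3.5 item 3 makes inducer washout mandatory and sends sites to Appendix E, and passing one exclusion bullet does not discharge that duty.

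Much of this stands. A careful site can satisfy all three texts, and section 3.5 partly answers which period to use. What remains is that the minimum is below the period of every listed inducer, so for those drugs it does no work, while it is the number that decides eligibility. The heading of Appendix E section 1 is phrased as a strong recommendation, but the text beneath it prohibits these inducers during the study.

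Two stronger readings are tempting and are not supported:

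- **Lost exposure in Cycle 1.** A reader might take the 14-day shortfall at s = 7 as the share of the 21-day Cycle 1 during which exposure is reduced. The Protocol gives no time course for the loss of induction and no size for the fall in concentration. Its statement concerns rifampicin given together with AZD9291, not rifampicin stopped a week or more before.
- **A 3-week washout already fits inside screening.** A reader might argue this from 21 < 28 days. Under the current text it does not follow, because section 3.5 item 3 puts discontinuation before screening begins.

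**Conclusion.** The point holds as a minor eligibility inconsistency. Criterion 2 admits, on its own terms, patients who fall short of the table it cites: 14 stop dates for a 3-week inducer and 28 for phenobarbitone. Section 3.5 item 3 narrows the gap but does not close it.

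The comparison of periods needs no outside assumption. The duplicate-entry point rests on common drug nomenclature, and the main finding stands without it. The 1-week rule for inhibitors is not contradicted.

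The Protocol does not say how many patients take these drugs; the number is probably small. A reader might infer that response could be biased. The documents do not support that, and no effect on ORR, sample size or analysis is claimed. The edition 4.0 changes mainly concern the final data cut-off and later follow-up, so the correction may now serve chiefly the eligibility record and any reuse of this wording.

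**What to change.** 1. **Section 3.2, criterion 2.** For inducers listed in Table 14, require at least 1 week or the Table 14 withdrawal period, whichever is longer, before first dose. Keep 1 week for inhibitors and unlisted agents.
2. **Section 3.5, item 3.** Replace the unquantified period before screening with the same period and the same first-dose anchor.
3. **Appendix E, Table 14.** Give phenobarbital and phenobarbitone one entry and one period, chosen by clinical pharmacology.

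The direct cost is wording in three places. For patients, a few with progressing disease may wait up to 14 more days than criterion 2 now requires, or 28 more for phenobarbitone if 5 weeks is kept. Against the minimum life expectancy of 12 weeks (84 days) in section 3.1, that is 14/84 = 17% or 28/84 = 33%.

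Moving the section 3.5 anchor to first dose also lets inducer washout run during screening, which the present text does not allow, so the sponsor should confirm that this is intended. Once moved, a 21-day period fits the 28-day window (section 5.1.1: "The baseline assessment should be performed within 28 days prior to treatment start"). A 35-day period exceeds it by 35 − 28 = 7 days, so the drug would have to be stopped at least 7 days before the window opens. Table 1 footnote c already permits consent before that window.

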3.3 Subject enrolment

Investigator(s) should keep a record, the subject screening log, of subjects who entered pre-study screening.

The Investigator(s) will:

1. Obtain signed informed consent from the potential subject before any study specific procedures are performed.
2. Assign potential subject a unique 7-digit enrolment number obtained through the IVRS/IWRS in the following format ECCNNXXX: CC being the country code, NN being the centre number and XXX being the patient enrolment code at the centre.

If a subject is re-screened, a new E-code will always be assigned. Any repeated tests and/or procedures will be performed as per documented local standards. Subjects will reconfirm their consent to participate in the study by resigning and dating their original consent form(s), next to their initial signature and date. A subject with a valid negative T790M result cannot be re-screened.

3. Determine subject eligibility. See Section 3.

At Visit 2, once the patient is confirmed to be eligible, the PI or suitably trained delegate will:

4. Perform a drug dispensing call in IVRS/IWRS.

If a subject withdraws from participation in the study, then his/her enrolment code cannot be reused.

3.4 Procedures for handling incorrectly enrolled subjects

Subjects who fail to meet the eligibility criteria should not, under any circumstances, be enrolled or receive study medication. There can be no exceptions to this rule. Subjects who are enrolled, but subsequently found not to meet all the eligibility criteria must not be initiated on treatment, and must be withdrawn from the study.

Where a subject does not meet all the eligibility criteria but is started on treatment in error, the investigator should inform the AstraZeneca study physician immediately, and a discussion should occur between the AstraZeneca study physician and the investigator regarding whether to continue or discontinue the patient from treatment. The AstraZeneca study physician must ensure all decisions are appropriately documented.

3.5 Restrictions

The following restrictions apply while the patient is receiving study treatment and for the specified times before and after:

1. Females of child-bearing potential should use reliable methods of contraception from the time of screening until 6 weeks after discontinuing study treatment. Acceptable methods of contraception include total sexual abstinence, tubal ligation, hormonal contraceptives that are not prone to drug-drug interactions [IUS Levonorgestrel Intra Uterine System (Mirena), Medroxyprogesterone injections (Depo-Provera)], copper-banded intra-uterine devices and vasectomised partner. All hormonal methods of contraception should be used in combination with the use of a condom by their male sexual partner for intercourse.
2. Male patients should be asked to use barrier contraceptives (ie, by use of condoms) during sex with all partners during the trial and for a washout period of 4 months. Male patients should avoid procreation for 4 months after completion of trial treatment. Patients should refrain from donating sperm from the start of dosing until 4 months after discontinuing study treatment. If male patients wish to father children they should be advised to arrange for freezing of sperm samples prior to the start of study treatment.
3. Once enrolled all patients must try to avoid concomitant use of medications, herbal supplements and/or ingestion of foods with known potent inducers of CYP3A4 whenever feasible, but patients may receive any medication that is clinically indicated for treatment of adverse events. Such drugs must have been discontinued for an appropriate period before they enter screening and for a period of 3 months after the last dose of AZD9291. All concomitant medications should be captured on

the eCRF. Guidance on medicines to avoid, medications that require close monitoring and on washout periods is provided (see [Appendix E](#)).

4. If medically feasible, patients taking regular medication, with the exception of potent inducers of CYP3A4 (see above), should be maintained on it throughout the study period. Patients taking concomitant medications whose disposition is dependent upon BCRP and which have a narrow therapeutic index should be closely monitored for signs of changed tolerability as a result of increased exposure of the concomitant medication whilst receiving AZD9291. Guidance on medications to avoid, medications that require close monitoring and on washout periods is provided (see [Appendix E](#)).

Patients taking rosuvastatin (due to BCRP mediated increase in exposure) should have CPK levels monitored. If the patient experiences any potentially relevant AE suggestive of muscle toxicity including unexplained muscle pain, tenderness, or weakness, particularly if accompanied by malaise or fever, the rosuvastatin must be stopped and any appropriate further management should be taken

Patients taking warfarin should be monitored regularly for changes in prothrombin time or INR.

5. Patients who wear contact lenses must discontinue wearing their lenses if they have any mild to moderate eye symptoms (CTCAE grade ≤ 2) while receiving treatment with AZD9291 until at least one week after symptoms have resolved. If a patient has a recurrence of eye symptoms or experiences any severe (CTCAE grade ≥ 3) ocular events they must discontinue wearing their contact lenses until at least one week after treatment with AZD9291 is permanently discontinued. Patients must not use any eye drops or ointment for treatment of eye symptoms, unless agreed by a study doctor, at any time during the study until 1 week after AZD9291 has been permanently discontinued. Patient should consult the clinic promptly if they have any concerns.

